## 2.3 RISK/BENEFIT ASSESSMENT

### 2.3.1 KNOWN POTENTIAL RISKS

There are minimal risks associated with participation in this study. All components of the ADRD-PC program – palliative care consultation, transitional care procedures – have been previously established as evidence-based clinical interventions that improve outcomes for other serious illness populations. This risk is no greater than a similar risk encountered in all current healthcare involving hospital care for persons with late-stage ADRD and the varied treatment choices confronting their family caregivers.

The primary risk to people with ADRD is potential loss of confidentiality, as personal protected health information (PHI) will be collected.

- To protect against this risk, all collected data, including PHI, will be defined by the research protocol, and limited to research purposes. We will protect confidential medical information from EHR reviews by abstracting data directly into a secure database or onto coded paper forms separated from personal identifiers. Data will be entered in a password protected secure database, and all paper documentation will be maintained in locked files. The Sheps Information Technology group enables standard operating procedures required to secure the network and databases, including operational and technical controls. All servers are located within a hardened data center. Modes of communication between the study coordinating center at the University of North Carolina, and between Site-CRC, Site-PI and hospital attending physicians will be restricted to encrypted e-mail, secure text messages, or secure verbal communication to protect confidential health information.

The primary risk for family caregivers is potential emotional distress related to learning more about dementia prognosis and participation in goals of care decisions. Participation in the study, particularly in the intervention group, may draw family members' attention to ADRD as a serious and progressive illness, and ask them to consider the pros and cons of different treatment options. This risk is no greater than a similar risk encountered in all current healthcare involving hospital care for persons with late-stage ADRD and the varied treatment choices confronting their family caregivers. However, given the vulnerable characteristics of persons with ADRD and the level of strain documented for ADRD caregivers, training of site-based research staff and investigators will explicitly address this potential risk.

- To protect against emotional distress for the family caregiver, we will inform them of their right to skip interview items, pause during participation, or withdraw from the study at any time. During the course of data collection, the CRC may identify clinical concerns or extreme emotional distress expressed by the family caregivers. The Principal Investigator, Site-PI or other senior investigator will be available to provide timely guidance for response to these concerns.

All CRCs will be trained to notify Site-PIs for any caregiver who expresses extreme emotional distress in response to study participation activities such as consent or interview items, or scores  $> 4.1$  points average / 37 points summed score (one standard deviation above the mean) on the Emotional Distress Subscale of the Family Distress in Advanced Dementia scale. The instrument has construct validity established with correlation to depression scoring instruments. CRCs will follow-up with caregivers with a script asking about their access to current emotional support, and desire for additional access to mental health resources. If the caregiver expresses need for additional mental

health resources, the CRC will contact the Site-PI, who will assist the CRC in exploring level of need and identification of appropriate referral resources, which may include the family caregiver's primary care provider, the current hospital attending physician and social worker, or local mental health services.

### 2.3.2 KNOWN POTENTIAL BENEFITS

**Potential individual benefits:** Study participants in the intervention arm may benefit from the palliative care and transitional care services provided in ADRD-PC. Participants in both arms will report on their lived experience during study interviews and will receive high quality educational material on dementia caregiving. Thus, all participants may benefit from the increased opportunity to communicate about the experience of family caregiving for people with late-stage ADRD, and from educational materials provided.

**Potential societal benefits:** This study is the first RCT of a hospital-based dementia-specific palliative and transitional care intervention. For people with late-stage ADRD and their caregivers, there is an urgent need to improve outcomes of burdensome hospital transfers, symptom distress, shared decision-making, and caregiver distress. The study is responsive to the National Alzheimer's Project Act call for enhancements in quality of care for people with ADRD and their caregivers, and to NIA / NIH research priorities. Thus, potential benefits include enhanced understanding of interventions to improve the quality of palliative care and outcomes for people with late-stage dementia and their caregivers. If efficacious, ADRD-PC has potential to reduce suffering for millions of people living with ADRD and their caregivers.

### 2.3.3 ASSESSMENT OF POTENTIAL RISKS AND BENEFITS

The benefit to risk ratio is highly favorable in this study. First, the ADRD-PC intervention has low risk of harms, as it is composed of evidence-based and minimal-risk interventions which are shown to improve outcomes for other serious illness populations. Second, there are significant potential benefits to participants in both study arms.

## 3 OBJECTIVES AND ENDPOINT / OUTCOMES

| OBJECTIVES  | ENDPOINT / OUTCOMES   | JUSTIFICATION   |
|---|---|---|
| Primary   |   |   |
| To conduct a multi-site RCT of the ADRD Palliative Care (ADRD-PC) program of dementia-specific palliative and transitional care ( intervention arm ) vs publicly available educational material for dementia caregivers ( control arm ) to compare 60-day hospital transfers (hospitalization and | Number of emergency room visits + hospital admissions within 60 days after discharge from index hospitalization | Hospital transfers are common for persons with late-stage ADRD, and are burdensome and stressful for the person and their family caregivers. Evidence shows that some hospital transfers are avoidable because acute illness can be treated in lower intensity settings, OR because goals of care are more comfort-focused. |

| OBJECTIVES   | ENDPOINT / OUTCOMES   | JUSTIFICATION   |
|--|---|---|
| emergency room visits) for persons with late-stage ADRD ( primary outcome ).

Secondary |   |   |
| To compare patient-centered secondary outcomes between intervention and control arms                 | a) Palliative Care Domain Index
b) Symptom Management at End of Life in Dementia
c) Neuropsychiatric Inventory Questionnaire
d) Post-acute use of palliative care, hospice
e) NH transitions                      | Physical and neuropsychiatric symptom distress is common in late-stage ADRD, and worsens toward death. Post-acute access to palliative services can improve outcomes, while new nursing home transitions may be avoidable with added community-based services and supports. |
| To compare caregiver-centered secondary outcomes between intervention and control arms               | a) documented communication about prognosis and goal of care
b) shared-decision making about hospitalization and other major treatment decisions
c) Family Distress in Advanced Dementia scale
d) Zarit Burden scale | Family caregivers serve as surrogate decision-makers in late-stage ADRD. They experience poor quality communication in usual care. In addition, caregivers experience significant emotional strain relative to caregiving role.   |

## 4 STUDY DESIGN

### 4.1 OVERALL DESIGN

Study design is an RCT conforming to SPIRIT and CONSORT statements for trial methods and protocol. Our approach uses NIA standards for a multi-site efficacy trial (Stage II) of a protocolized behavioral intervention, while incorporating pragmatic features to support sustainability and future dissemination. We will use 1:1 randomization of patient-caregiver dyads with concealed allocation until study assignment. Research will occur at 5 geographically diverse sites of the Palliative Care Research Cooperative (PCRC) network, with study leadership and centralized IRB at UNC. Sites will enroll N=424 dyads of hospitalized patients with late-stage ADRD (GDS 6-7 or GDS 5 with significant co-morbidity) with their family caregivers. Sites will additionally enroll N=50 dyads that identify as Hispanic/Latino. Intervention dyads will receive the ADRD-PC program of i) dementia-specific palliative care, ii) standardized caregiver education, and iii) transitional care. Control dyads will receive publicly available educational material on dementia caregiving. Outcomes will be measured at 30 days (interim) and 60 days post-discharge. The primary outcome will be 60-day hospital transfers, defined as visits to an emergency department or hospitalization (**Aim 1**). Secondary patient-centered outcomes will be symptom treatment, symptom control, use of community palliative care or hospice, and new nursing home transitions (**Aim 2**). Secondary caregiver-centered outcomes will be communication about prognosis and goals of care, shared decision-making about hospitalization and other treatments, and caregiver distress (**Aim 3**). The Principal Investigator

and outcome assessors will be masked; as in most behavioral interventions clinicians and participants cannot be masked to study arm. Analyses will use intention-to-treat, and pre-specified exploratory analyses will examine effects of sex as a biologic variable, race / ethnicity, and GDS stage.

## 4.2 SCIENTIFIC RATIONALE FOR STUDY DESIGN

We conducted a pilot RCT, randomizing 62 dyads of hospitalized patients with GDS 5-7 ADRD and their family caregivers to the ADRD-PC program vs usual care with publicly available education material. While underpowered to show a difference in 60-day hospital transfers, we found marked differences in intermediate outcomes. Intervention dyads were more likely to have an active POLST advance directive (79% vs 30%,  $p<0.001$ ) and to make a decision to avoid future hospitalization (13% vs 0%,  $p=0.033$ ). With ADRD-PC, persons with late-stage ADRD had more palliative care domains addressed in their treatment plan (Palliative Care Domain index score 7.6 vs 2.7,  $p<0.001$ , range 0-10), and symptom management for dyspnea (77% vs 34%,  $p<0.001$ ), constipation (93% vs 25%,  $p<0.001$ ), depression (83% vs 25%,  $p<0.001$ ) and delirium (80% vs 19%,  $p<0.001$ ). Caregivers were more likely to discuss prognosis (90% vs 3%,  $p<0.001$ ) and goals of care (90% vs 25%,  $p<0.001$ ). Intervention dyads also increased use of post-discharge palliative care (21% vs 7%,  $p=0.124$ ) and hospice (25% vs 3%,  $p<0.019$ ). Results indicate the potential for ADRD-PC to improve patient and caregiver-centered outcomes, including hospital transfers.

## 4.3 JUSTIFICATION FOR INTERVENTION

Our preliminary studies justify the proposed RCT. First, we have created novel and effective methods to find and recruit dyads in hospital. Second, ADRD-PC is feasible and acceptable to people with ADRD, caregivers and clinicians. Third, palliative care clinicians deliver the ADRD-PC program with high fidelity, ranging from 77% (two follow-up calls) to 93% (dementia-specific palliative care, standardized education). Fourth, we used best practices to optimize enrollment and retention. Fifth, pilot data support relevance of ADRD-PC to persons with GDS 5-7, as in our pilot trial all stages enrolled equally, had similar death rate, and all 60-day hospital transfers affected GDS 5-6. Sixth, results show ADRD-PC improves intermediate outcomes strongly linked to hospital transfers. Thus, the necessary next step to advance the science of dementia-specific palliative care is an adequately powered RCT of the ADRD-PC program to test efficacy to improve patient and caregiver centered outcomes.

## 4.4 END-OF-STUDY DEFINITION

The end of the study is defined as completion of the 60-day EHR chart review for all dyads.

## 5 STUDY POPULATION

### 5.1 INCLUSION CRITERIA

Target enrollment is N=424 dyads of people with late-stage dementia and their family caregiver, and N=50 dyads that identify as Hispanic/Latino.

People with ADRD will be eligible if they are: (1) aged 55 or older, (2) hospitalized, (3) have a physician-confirmed diagnosis of ADRD, and (4) staged GDS 6 or 7; or GDS 5 with additional

co-morbidity defined by Charlson Comorbidity Index scored 5 or higher. As in the pilot, ADRD stage will be confirmed by the attending physician and caregiver.

Caregivers will be eligible if they are: (1) the adult (aged 18 or older) legally authorized representative (LAR) for healthcare and have capacity to serve in this role, (2) support the person with ADRD, and (3) can complete interviews in English or Spanish. As in our prior ADRD research, other family caregivers may be present per primary caregiver request, but only the primary caregiver is a participant.

## 5.2 EXCLUSION CRITERIA

Dyads will be excluded if (1) the LAR is not a family caregiver, (2) the patient currently receives palliative care or hospice, (3) patient or caregiver would be unduly stressed, or (4) dyad is not successfully randomized.

## 5.3 STRATEGIES FOR RECRUITMENT AND RETENTION

Recruitment and retention of seriously ill patients with stressed caregivers is challenging, and can threaten validity. We will train all sites in the Palliative Care Research Collaborative best practices to assure compliance with research ethics standards, complete and timely case-finding, compassionate approach and messaging, and flexibility to accommodate caregivers.

Participant screening: Site-CRCs will use an EHR algorithm for rapid case-finding. This method, developed during the pilot research, generates daily automated EHR lists of newly hospitalized patients with ADRD. Site-CRCs will conduct brief chart reviews under a HIPAA waiver to confirm eligibility criteria and forward patients with probable late-stage ADRD to the Site-PI for review. After brief EHR reviews by Site-CRCs and Site-PIs to confirm eligibility, Site-PIs will contact the inpatient attending physicians. They will confirm GDS stage as 5, 6 or 7, and seek permission to approach caregivers.

Recruitment and informed consent: Recruitment will utilize diverse communication approaches with family caregivers; these approaches are identical to clinical communication used with family caregivers for people with dementia who lack decisional capacity. Since family caregivers may be present in hospital, or may be barred from visitation due to COVID-19 restrictions and safety concerns, or may live at a great distance from the hospital, recruitment and enrollment procedures will include both in-person and telephone / virtual communication methods. Further, flexibility of communication is essential for the enrollment of the project number of participants, because study enrollment and participation in the ADRD-PC intervention must both occur during acute illness hospitalization.

Site-CRCs will introduce the study to eligible family caregivers using scripted telephone calls or in-person visits. When the Site-CRC conducts recruitment and enrollment via telephone, the Site-CRC will ask if the individual is in a private location, and feels comfortable talking about the study at that time; they will schedule an alternative time if necessary. The Site-CRC will explain the study over the phone using a telephone script. Spanish-speaking CRCs will introduce and explain the study to any Spanish-speaking participants using translated recruitment scripts and study materials.

If the family caregiver is interested and wants to participate, the Site-CRC will conduct the informed consent with them verbally in person or over the phone. If the family caregiver agrees to consent, study informational materials and the informed consent form will be sent to them by mail or secure e-mail.

Due to the low risk of study participation and the restrictions on immediate written consent described above, verbal consent will be accepted for participation in the enrollment caregiver interview, and for randomization with initiation of the ADRD-PC or control conditions.

Site-CRCs will introduce the study in scripted introductory phone calls or in-person visits. After informed consent, the caregiver will complete the enrollment interview.

**Retention:** Retention is supported first and foremost by respectful, flexible, and compassionate interpersonal encounters with site-based research staff which will be consistently emphasized in training and coaching communication. Secondly, retention is supported by setting appointments for follow-up interviews with recognizable Site-CRC names and contact information. Third, retention is supported by obtaining multiple contact information for family caregivers. And fourth, retention is promoted by small payments for completion of study visits. Family caregivers will receive a \$25 gift card for completing each of the three interviews (enrollment, 30-day, and 60-day follow-up), for a total of \$75.

## 6 STUDY INTERVENTION AND CONTROL CONDITIONS

### 6.1 STUDY INTERVENTION

**Intervention Condition:** Patient-caregiver dyads randomized to the intervention will receive the ADRD-PC program, described below and in Table 1.

#### Delivering the ADRD-PC Program

| Elements                          | Content  | Method of Delivery  |
|-----------------------------------|--|---|
| Dementia-specific Palliative Care | 
 
1) Prognosis – exploration and communication of stage, trajectory and prognostic awareness
 
2) Symptoms – assessment and treatment for physical and neuropsychiatric symptoms
 
3) Shared decision-making – exploration of values and goals of care; discussion of treatment decisions
 
4) Transitional care – assessment of needs, care planning and recommendation for support services
 
 | 
 
* Interdisciplinary palliative care clinicians meet with the person with ADRD and family caregiver.
 
* ADRD-PC Note Template used to record encounters addressing these 4 domains
 
 |
| Standardized Caregiver Education  | 
 
1) Dementia and its stages
 
2) Determining the primary goal of care
 
3) Approach to decision-making
 
4) Approach to eating problems
 
5) Approach to decisions about hospitalization
 
6) Approach to decisions for infections
 
7) How dementia affects the family
 
8) What is hospice and palliative care?
 
  | 
 
* Clinicians share booklet Advanced Dementia: A Guide for Families and individualize content during counseling for prognostic awareness and decision-making
 
                               |
| Transitional Care                 | 
 
1) Palliative Care Plan – written summary of dementia stage and prognosis, recommendations for symptom
 
   | 
 
* Palliative Care Plan addressing 4 domains provided to the
 
   |

|  |  |   |
|--|--|---|
|  | 
treatment, goals of care and treatment decisions, and for support services.
 
2) New referrals to support services – examples include community palliative care, hospice, home health, geriatric clinic, dementia clinic, caregiver support group, adult day care, support group.
 
3) Contact information for the palliative care team
 | 
outpatient clinician AND caregiver
 
* Referrals to community support services
 
* Post-discharge supportive calls at 72 hours and 2 weeks
 |
|--|--|---|

- 1) **Dementia-specific palliative care** will be delivered by hospital-based specialty interdisciplinary palliative care teams. Encounters will include a physician or advanced practice provider and at least one additional discipline (nurse, social worker, chaplain). Visits will continue until hospital discharge, and will be documented in the EHR with the ADRD-PC Note Template. Palliative care clinicians will address four domains. First, the palliative care team will promote caregivers' **prognostic understanding** of dementia stage and its trajectory, contextualizing the acute illness with information about ADRD. Second, the palliative care team will conduct ADRD-specific **symptom management** of pain, other physical and neuropsychiatric symptoms, and recommend treatment consistent with best practices for ADRD. Third, the palliative care team will facilitate **shared decision-making** with the caregiver. Discussions may include exploration of overall goals of care, and decision-making about potentially burdensome treatments of resuscitation, ventilator use, feeding tubes, antibiotics, or future hospitalizations. When clinically appropriate, consultation will also include completion of new advance directives such as a Physician Orders for Life Sustaining Treatment (POLST) or comparable portable order set to document decisions for current care plans. POLST or similar documentation is in all study states and enhances treatment matched to patient preferences across healthcare transitions. Fourth, the palliative care team will assess **transitional care needs for community support services**. They will support dyads with post-discharge follow-up calls and referral to community services. (see Transitional care).
- 2) **Standardized caregiver education** will be provided by the palliative care team. Clinicians will share and discuss the booklet Advanced Dementia: A Guide for Families, which addresses common concerns and treatment decisions. Clinicians will individualize its content, highlighting key content and providing counseling about its relevance for current or future caregiving and treatment decision-making.
- 3) **Transitional care** will be provided by the palliative care team. Pre-discharge, the palliative care team will explore **adequacy of patient and caregiver support for practical, emotional and spiritual needs**. Based on needs, they will recommend **community-based support services**. Examples could include community palliative care, hospice, home health, specialty geriatric or dementia clinics, adult day care or Alzheimer caregiver support groups. Near discharge, a member of the palliative care team will create a templated Palliative Care Plan and provide copies to the primary or post-acute care provider (PACP) AND the family caregiver. This document will summarize recommendations in the four domains and provide contact information for the palliative care team for follow-up questions. Post-discharge, a designated palliative care team member – usually a social worker or nurse coordinator – will call the family caregiver within 72 hours and again within 2 weeks after discharge. These calls may also be facilitated by a site CRC. The purpose of these calls will be to support implementation of the Palliative Care Plan and access to post-acute

supportive services. Calls will also be used to solicit concerns, offer emotional support, and make recommendations to help the caregiver overcome barriers to services.

**Control condition:** Patient-family caregiver dyads randomized to the control arm will receive educational materials from the Alzheimer's Association, specifically designed for late-stage ADRD caregivers. The patient will receive usual hospital and post-acute care.

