### 6.3 MEASURES TO MINIMIZE BIAS: RANDOMIZATION AND MASKING

Randomization will occur following the enrollment interview, with the dyad as the unit of randomization and analysis. Allocation will be concealed prior to randomization. Randomization will be generated within REDCap software, and transmitted by the Site-CRC to the PC team to initiate ADRD-PC (intervention) or to deliver dementia caregiver educational material (control).

CRCs who collect outcome data will be masked to study arm in family caregiver interviews. Since the EHR will have ADRD-PC palliative care encounters, Site-CRCs will complete follow-up EHR reviews only after 60-day follow-up interviews. [name] (PI) will remain masked to study arm assignments to minimize bias in study procedures and analysis.

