### **Electronic Health Record Review:**

1. Symptom assessment and management plans during hospitalization-
  - a. Palliative Care Domain Index Items
2. Documented discussion of dementia prognosis
3. Documented discussion decision-making for goals of care
4. New nursing home transfers
5. Return to acute care – ED or Hospital readmissions within 60 days and up to 3 reasons for return

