## 9 STATISTICAL CONSIDERATIONS

### 9.1 STATISTICAL HYPOTHESES

**Aim 1:** To conduct a multi-site RCT of the ADRD-PC program (**intervention arm**) vs publicly available educational material for dementia caregivers (**control arm**) to compare 60-day hospital transfers (hospitalization and emergency room visits) for persons with late-stage ADRD (**primary outcome**). **H1:** *60-day hospital transfers will be lower in the intervention vs. control arm.*

**Aim 2:** To compare patient-centered secondary outcomes between intervention and control arms: a) symptom treatment (Palliative Care Domain index); b) symptom control (Symptom Management at the End of Life in Dementia scale, Neuropsychiatric Inventory Questionnaire); c) post-acute use of community palliative care or hospice; and d) new nursing home transitions. *Patients in intervention vs. control arms will have better symptom treatment (H2a) and symptom control (H2b); increased use of community palliative care or hospice (H2c); and fewer new nursing home transitions at 60 days post-discharge (H2d).*

**Aim 3:** To compare caregiver-centered secondary outcomes between intervention and control arms: a) communication about prognosis and goals of care; b) shared decision-making; and c) caregiver distress (Family Distress in Advanced Dementia scale and Zarit scale). *Caregivers in intervention vs control arms will more often have documented communication about prognosis and goals of care (H3a); report more shared decision-making about hospitalization and treatments (H3b); and report less caregiver distress at 60-days post-discharge (H3c).*

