### 9.2 SAMPLE SIZE DETERMINATION

Based on prior ADRD research, we project 15% dropouts (death, withdrawal) equally distributed between groups; caregiver data collection is completed after deaths as in our prior ADRD

research. Total sample size for analysis of 60-day follow-up outcomes is thus n=360. All statistical tests will be 2-tailed with an overall 0.05 significance level for pre-specified analyses. Statistical power is based on a 2-sided alpha of 0.05 significant tests and using standard deviation estimates from our pilot study (**Table 3**).

Power calculations assume a “best guess” 15% dropout (death, withdrawal) rate based on prior ADRD research (n=180 per group at 60-day follow-up) and a “worst case” 25% dropout rate (n=159 per group). These rates consider 9% patient mortality and 92% caregiver retention rate in the pilot. In our pilot data, 0.52 is the lower bound of the 95% CI for the IRR comparing

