#### 9.4.3 ANALYSIS OF THE SECONDARY ENDPOINT(S)

**Aim 2:** To compare patient-centered secondary outcomes between intervention and control arms: a) symptom treatment (Palliative Care Domain index); b) symptom control (Symptom Management at the End of Life in Dementia scale, Neuropsychiatric Inventory Questionnaire); c) post-acute use of palliative care or hospice; and d) transition to nursing home care.

Analysis to Meet Aim 2: We will compare study arms during 60 days post-discharge on the following outcomes:

2.a. Symptom treatment: This ordinal outcome is the summation of presence (=1) or absence (=0) of 10 domains of palliative care. We will treat it as a continuous variable due to a high variation observed in the pilot data. We will use Student's t-test to compare the mean difference between study arms unless violation of assumptions warrants the Mann-Whitney test. We will use a multiple linear regression model with main effects for treatment group, study site, GDS Stage and patient and caregiver sex as a biological variable.

2.b. Symptom control: We will use Symptom Management (SM-EOLD) scale to measure caregiver report of patients' uncontrolled symptom distress and Neuropsychiatric Inventory Questionnaire (NPI-Q) to measure caregiver report of patients' neuropsychiatric symptom distress. Linear mixed models with random intercepts for patients will be used with a time indicator (30 vs 60 days follow-up) with the above main effects.

2.c. Use of post-acute palliative care or hospice: This outcome will be defined by whether patients ever use hospice or outpatient palliative care during the time from discharge to 60 days follow-up. We will compare the proportions using Pearson's chi-square test. Logistic regression will be used for multivariable modeling with the same main effects as in Aim 2.a. Final estimates will be reported as covariate-adjusted odds ratios.

2.d. Transition to nursing home care: This outcome will be defined by whether patients transition to nursing home care during the time from discharge to 60 days follow-up. We will compare proportions using Pearson's chi-square test. Logistic regression will be used for multivariable modeling with the same main effects as in Aim 1. Final estimates will be reported as covariate-adjusted odds ratios.

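### H2a and H3a are abstracted unmasked from a chart in which only the intervention arm is described as using a note template, so a difference mixes real care with delivery and fuller recording

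*Combined protocol and SAP*

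**What the plan says.** **Source of the outcomes.** The Schedule of Activities (1.2) and the Electronic Health Record Review list in 8.1 take the Palliative Care Domain Index and both documented-discussion items from the EHR alone. The index items are described there as "Symptom assessment and management plans during hospitalization". Section 9.4.3 scores the index as a count of 10 domains, each present or absent.

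**What goes into that chart.** In the intervention arm, 6.1 has the palliative care team record its visits in the EHR on a dedicated form: "ADRD-PC Note Template used to record encounters addressing these 4 domains". The four domains are prognosis, symptoms, shared decision-making (including goals of care) and transitional care. A templated Palliative Care Plan summarises the same four. Controls receive educational material and usual care, and no template is described for them. Section 6.2.1 also reviews a 10% sample of the intervention notes for fidelity across the four domains.

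**Masking.** Section 4.1 says outcome assessors are masked. Section 6.3 promises this for caregiver interviews, then adds: "Since the EHR will have ADRD-PC palliative care encounters, Site-CRCs will complete follow-up EHR reviews only after 60-day follow-up interviews".

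**Hypotheses and window.** Under H2a, intervention patients "will have better symptom treatment (H2a"). H3a is worded as documented communication. The analysis of 2a to 2d in 9.4.3 opens: "We will compare study arms during 60 days post-discharge on the following outcomes".

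**The concern.** The two arms are charted differently by design, and the outcome is what the chart says. A template that prompts for prognosis, symptoms and goals of care makes it more likely that a discussion or plan is written down where an abstractor will find it. In the control arm, the same care given but not charted scores as absent. The abstractor can also see which arm the chart belongs to. Delaying chart review until after the 60-day interview protects the interview and not the abstraction.

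What is at stake is the conclusion drawn. H2a is worded as better symptom treatment, but 8.1 collects assessments and plans, not treatment received or symptom response. H3a is worded as documented communication in Sections 3 and 9.1, but the synopsis, the Aim 3 statement and 9.4.3 drop the qualifier. Section 4.2 already reads the pilot chart result as caregivers being more likely to discuss prognosis. A report following that pattern would claim more than the measure supports.

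The window for 2a is also inconsistent: during the hospital stay in 8.1, when the intervention is being delivered, but after discharge in 9.4.3.

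**Working it through.** **1. The plan's own power figures.** Inputs from 9.2 and Table 3: "All statistical tests will be 2-tailed with an overall 0.05 significance level for pre-specified analyses"; 1:1 allocation; "n=180 per group at 60-day follow-up" at 15% dropout and 159 at 25%.

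For two means, power = Φ(δ / (σ√(2/n)) − 1.96). For the index with δ = 0.5, σ = 1.7, n = 180: 0.5 / (1.7 × 0.1054) = 2.79, and Φ(0.83) = 0.797. For two proportions the pooled-variance form was used.

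| Row | Difference | Stated (15% / 25%) | Recomputed |
|---|---|---|---|
| PC Domain Index | 0.5 points | 0.80 / 0.75 | 0.797 / 0.746 |
| Prognosis discussion | 3% vs 11% | 0.85 / 0.80 | 0.848 / 0.801 |
| Goals-of-care discussion | 25% vs 39% | 0.82 / 0.77 | 0.815 / 0.766 |

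At the larger Table 3 differences all three exceed 0.99, as stated. The arithmetic is sound. The question is what is being measured.

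**2. Pilot figures (4.2, 4.3).** The index was 7.6 vs 2.7, a gap of 4.9 points, or 4.9 / 1.7 = 2.9 SD. Prognosis discussion was 90% vs 3% and goals of care 90% vs 25%. Delivery of the palliative care component was 93%. The smallest index difference in Table 3 is 0.5 / 4.9 = 10% of the pilot gap. That corresponds to one extra domain marked present in every second intervention patient.

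**3. What recording alone could do (assumed values, not in the documents).** Suppose the true discussion rate q is the same in both arms, template notes capture 95% of discussions, usual notes capture 80% or 50%, and n = 180 per arm. The recorded rate is q × capture. The chance of a significant result is:

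| q | Recorded, intervention | Control at 80% capture | P(significant) | Control at 50% capture | P(significant) |
|---|---|---|---|---|---|
| 10% | 9.5% | 8% | 7% | 5% | 38% |
| 25% | 23.75% | 20% | 14% | 12.5% | 79% |
| 50% | 47.5% | 40% | 30% | 25% | >99% |
| 90% | 85.5% | 72% | 88% | 45% | >99% |

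With equal capture it stays at 5%.

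**4. Can recording alone explain the pilot?** The capture needed in usual notes is the observed control rate divided by q. For the 3% control prognosis rate it is 0.03 / 0.25 = 12% at q = 25%, and 0.03 / 0.90 = 3% at q = 90%. Usual notes would have to miss nearly every discussion.

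**5. Does a completed template simply fill the index?** If it did, and undelivered dyads scored like controls, the pilot intervention mean would be about 0.93 × 10 + 0.07 × 2.7 = 9.5. It was 7.6.

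**The case against.** A reader might infer that H2a and H3a measure only delivery, that they cannot show any improvement in care, or that a positive result is nearly guaranteed by the template. The documents do not support that, for these reasons:

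- A template note records a real visit by a physician or advanced practice provider with a second discipline, including symptom recommendations (6.1). Steps 4 and 5 also go against a pure recording effect.
- The 10 index domains and the template fields are not listed, so full overlap is unproven. It is established only that the template covers prognosis, symptoms and goals of care.
- The similarity of 90% and 93% would also arise if consultations genuinely led to discussions. Power above 0.99 at the pilot differences also appears in other Table 3 rows, such as hospice use and SM-EOLD, so it is no sign of circularity.
- The fidelity overlap is partial. Note review covers 10% and scores quality, whereas the index is a present/absent count in every dyad.
- H3a is already worded as documented communication, which a chart can show. Symptom control (H2b) and shared decision-making (H3b) come from caregiver interviews.

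Two strong remedies would also add bias of their own. Scoring only outside the template discards, in one arm, the notes where the plans and discussions are held. Replacing H3a with caregiver report relies on unmasked caregivers recalling hospital conversations 30 to 60 days later.

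All of this stands, and it limits the point to interpretation. It does not remove the asymmetry in charting, the unmasked abstraction, the wording of H2a or the conflict over the window. Nor does the listed interview content include an item on prognosis communication.

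**Conclusion.** The concern holds in a limited form. A between-arm difference on H2a or H3a combines real care and communication with delivery of the intervention and more complete recording, and the plan has no rule that separates them. Such a difference supports a conclusion about documented process of care. Alone, it does not establish better symptom treatment or better communication as caregivers experience it.

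The size of the bias is unknown, because it depends on how completely usual notes capture care and the documents give no figure for that. Over the assumed range in step 3, recording alone yields a significant result anywhere from 7% to more than 99% of the time. Part of the pilot gap is probably real. These are secondary outcomes, and the primary outcome, hospital transfers, is not affected.

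**What to change.** 1. Keep the planned comparisons, but label 2a and 3a as process-of-care or documentation outcomes in Sections 3, 9.1 and 9.4.3. Reword H2a to documented symptom assessment and management plans. Rest any claim of symptom benefit on H2b (SM-EOLD and NPI-Q, both caregiver-reported). Table 3 gives SM-EOLD power of 0.80 for 2.3 points at 15% dropout, which reproduces as 0.799.
2. Reconcile 8.1 and 9.4.3 to one window for 2a, the index hospitalization.
3. Correct 4.1 to say that EHR abstraction is not masked. Record the source note for each abstracted item. Add a sensitivity analysis that excludes the ADRD-PC template notes and the Palliative Care Plan. State that it is biased against the intervention, so that it serves as a lower bound with respect to note source and does not replace the main scoring.
4. Optionally, add a caregiver-reported item on prognosis and goals discussion to the existing 30- and 60-day interviews, as support for H3a and not a replacement.

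**Cost.** Items 1 and 2 are wording. Item 3 needs one extra abstraction field and one extra analysis. Item 4, if taken up, needs IRB approval and a Spanish version. The downside is that two very large expected effects will support a narrower conclusion. Randomization, intervention and sample size do not change.
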